3.4 Study Hypotheses

We hypothesize that an adequately powered RCT to test whether vitamin K treatment inhibits the progression of CAC in patients with ESKD requiring HD treatment will be feasible (see section 7.1.1).

We hypothesize that vitamin K treatment will improve vitamin K biomarkers, reduce inflammation, prevent progression of CAC and valve calcification, reduce bone fracture, and improve body composition over 12 months.

4 Study Methods

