5.2 Analysis Populations

All analyses will use a modified intent-to-treat population using all available data. However, one patient who developed an exclusion criteria post-randomization but did not receive any study intervention will be excluded from primary analysis. Thus, all randomized patients will be analyzed in the arm they were randomized to regardless of treatment compliance or data completion.

6 Trial Population

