7.1 Outcome Definitions

7.1.1 Feasibility Outcomes (Primary)

The pre-specified primary outcomes are as follows:

	Outcome	Definition	Target
1	Recruitment rate	Number of participants recruited per month at each site (total eligible randomized patients per site divided by date of last randomized patient at that site minus date of first randomized patient at that site, with month defined as 30.4 days. This will exclude first phase of KGH enrollment), as well as an overall crude average of each site’s rate.	>4.17 per month
2	Compliance with study medication	Proportion of prescribed doses received (divide received doses by prescribed for each patient to get a patient level measure before summarizing).	≥90% of prescribed
3	Dropout rate	Proportion of participants who dropped out from the trial (1-[% of randomized patients who either have a known date of death during the study period OR have a non-missing CAC value measured at least 6 months after randomization]).	<20%
4	Adherence to study protocol	Proportion of participants who adhered to the study protocol (90% study medication compliance and not dropped out) (all pooled).	≥80%
5	Rates of eligible patients consented and randomized	Proportion of eligible patients who were A) consented and B) randomized to the study.	No target

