7.1.2 Secondary Outcomes

- 1) Coronary artery calcification progression:
 - a) the percent and absolute change of the Agatston and volume calcium scores (CT scan) will be assessed at study exit vs. baseline. Included measures will be: Total CAC, Left Main CAC, Right Coronary Artery CAC, Left Anterior Descending CAC, Circumflex CAC, and Posterior Descending Artery CAC.
 - b) the proportion of participants with a 15% or greater increase in Agatston and volume calcium scores will be assessed at study exit vs baseline.
- 2) Coronary artery calcification regression: the proportion of participants with a 10% or greater decrease in Agatston and volume calcium scores will be assessed at study exit vs baseline.
- 3) Aortic valve calcification progression: the absolute and percentage change of the Agatston and volume calcium scores (CT scan) will be assessed at study exit vs. baseline.
- 4) Mitral valve calcification progression: the absolute and percentage change of the Agatston and volume calcium scores (CT scan) will be assessed at study exit vs. baseline.
- 5) AAC score: the AAC score (mean score in L1-L4, mean number of positive segments, mean total severity using lateral lumbar spine radiographs) will be assessed at study exit vs. baseline.
- 6) Biomarkers of vitamin K status: Gas6, PK, MK4, osteocalcin Gla, osteocalcin Glu, osteocalcin Gla to Glu ratio, percent of osteocalcin undercarboxylated, and dpucMGP will be assessed at baseline, four, eight and study exit. PIVKA-II will be assessed at baseline and study exit.
- 7) Thoracic vertebral fractures: The prevalence and incidence of thoracic vertebral fractures (anterior and lateral radiographs) will be assessed at baseline and study exit.
- 8) Lumbar vertebral fractures: The prevalence and incidence of lumbar vertebral fractures (anterior and lateral radiographs) will be assessed at baseline and study exit.
- 9) Events of clinical interest:

The presence or absence and total of the following events will be assessed across the study duration per patient:

 - i) Hospitalizations
 - ii) Cardiovascular events: acute coronary syndrome, congestive heart failure, stroke, transient ischemic attack, amputation, and cardiac (symptom-driven) (cerebral or peripheral) revascularization procedure, or cardiac arrest
 - iii) Thrombosis: deep vein thrombosis and pulmonary embolism
 - iv) HD access thrombosis. Fistula and/or graft thrombosis or dialysis catheter thrombosis
 - v) Mortality: all-cause and cardiovascular cause

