7.2 Analysis Methods

The feasibility outcomes will be presented descriptively overall as rates or proportions. In addition, compliance with study medication, dropout rate, and adherence to study protocol will be compared by arm. Reasons for loss-to-follow-up and non-compliance will be tabulated.

For the binary outcomes, we will provide counts and percentages by arm and compare arms by the Mantel-Haenszel test stratified by site and diabetes (or Fisher's Exact Test for outcomes with less than 20 events or non-events).

This study has many continuous outcomes that are far from normally distributed. For all continuous outcomes, we will report medians and quartiles by arm and compare arms by the Van Elteren test stratified by site and diabetes. Selected continuous variables may be depicted by clustered boxplots comparing the two arms over time. Biomarkers assessed at multiple time points will have both absolute value and change from baseline compared by arm at each time point.

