7.3 Missing Data

The number of missing items will be presented by arm for each outcome. Imputation will not be performed for this feasibility/phase II pilot study.

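### Non-fatal clinical events are compared without regard to follow-up time, so unequal early exit or death between arms would distort the comparison

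*SAP*

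**What the plan says.** Item 9 of SAP section 7.1.2 covers hospitalizations, cardiovascular events, thrombosis, dialysis access thrombosis and mortality. Its measure is: "The presence or absence and total of the following events will be assessed across the study duration per patient".

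Section 7.2 gives two methods. For yes/no outcomes: "For the binary outcomes, we will provide counts and percentages by arm", and it will "compare arms by the Mantel-Haenszel test stratified by site and diabetes", with Fisher's exact test when events or non-events are few. For continuous outcomes: "we will report medians and quartiles by arm and compare arms by the Van Elteren test stratified by site and diabetes". Totals per patient are not named there, but this is the only method offered for anything that is not binary.

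Three other provisions bear on follow-up:

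- Section 5.2, which excludes one patient, says that "all randomized patients will be analyzed in the arm they were randomized to regardless of treatment compliance or data completion".
- Section 7.1.1 counts as not dropped out those who "have a known date of death during the study period OR have a non-missing CAC value measured at least 6 months after randomization".
- Section 7.3 states: "Imputation will not be performed for this feasibility/phase II pilot study".

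The SAP contains no person-time rate, censoring rule, time-to-event method or treatment of death as a competing event for item 9. The Appendix A checklist marks sensitivity analyses as not applicable.

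**The concern.** The hypotheses in section 3.4 refer to effects such as to "improve body composition over 12 months", so the intended observation period is a year. Actual follow-up will vary. The dropout target tolerates just under 20%. Deaths do not count as dropout, and neither does a patient whose last scan was at month 6. Shortened follow-up can therefore exceed 20% of patients even when the target is met.

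A patient observed for three months has less opportunity to be hospitalized than one observed for twelve, yet both enter the comparison on the same footing. If one arm loses more patients early, its non-fatal events fall for that reason alone. The error favours the arm with more withdrawals or deaths.

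Two uses are at stake. Checklist item 30 (harms) points to page 12, within the page range given for outcome definitions, so item 9 probably carries the harm comparison; that is an inference. The pilot is also meant to inform a definitive trial, whose planning needs event rates with a known amount of observation behind them.

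**Working it through.** **The plan's own nearest figure.** Section 4.3 states at least 80% power for a 30-point difference in proportions with 40 per arm. In the least favourable case, 35% v 65%, the unpooled normal formula gives a standard error of √[(0.35×0.65 + 0.65×0.35)/40] = 0.1067. Then 0.30/0.1067 − 1.96 = 0.85, which is 80.3% power. The figure reproduces under that formula, which treats every patient as fully observed.

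**Inputs.** From the SAP: 40 per arm, two-sided 0.05, 12 months. Assumed, because the SAP gives neither: true rate λ of 0.5 or 1.0 events per patient-year, identical in both arms, and a fraction d leaving early. Exit is unrelated to risk, and events are not recorded after exit.

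**Formulas.**

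- Exit at 3 months: P(any) = (1−d)(1−e^−λ) + d(1−e^−λ/4); mean total = λ(1−0.75d).
- Exit spread evenly over the year: P(any) = (1−d)(1−e^−λ) + d[1−(1−e^−λ)/λ]; mean total = λ(1−d/2).

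Example, λ = 1 and d = 0.2 at 3 months: 0.8×0.632 + 0.2×0.221 = 0.550, against 0.632 with no early exit.

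| Early exit | λ | Any event | Gap (points) | Ratio of totals |
|---|---|---|---|---|
| 0% v 20%, at 3 months | 1.0 | 63.2% v 55.0% | 8.2 | 0.85 |
| 0% v 20%, at 3 months | 0.5 | 39.3% v 33.8% | 5.5 | 0.85 |
| 0% v 20%, spread evenly | 1.0 | 63.2% v 57.9% | 5.3 | 0.90 |
| 0% v 20%, spread evenly | 0.5 | 39.3% v 35.7% | 3.6 | 0.90 |
| 10% v 20%, spread evenly | 1.0 | 60.6% v 57.9% | 2.6 | 0.95 |
| 10% v 20%, spread evenly | 0.5 | 37.5% v 35.7% | 1.8 | 0.95 |
| 20% v 20%, either pattern | either | equal | 0 | 1.00 |

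**False positives.** These come from 4,000 simulated trials per scenario, with an unstratified rank test and a two-proportion test standing in for the stratified tests. With 0% v 20% leaving at 3 months, rejection is about 11% at λ = 1.0 and about 8% at λ = 0.5. With equal exit it is about 5%. With a 10-point imbalance spread evenly it is no more than about 6%.

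**Withdrawals and deaths together.** Take dropout of 20% v 5% plus deaths of 20% v 10%, λ = 1, and between-patient variation in risk (gamma, shape 1.5). Mean totals are 0.81 v 0.93 (0.81/0.93 = 0.87), any event is 46% v 50%, and the rank test rejects about 7.5%.

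**What person-time does.** Expected events and expected follow-up shrink together, so events per patient-year are equal between arms in all these scenarios. If exit instead becomes likelier as a patient's risk rises, totals are 0.72 v 0.88 and rates 0.88 v 0.95. The false reduction is smaller but still there.

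**The case against.** The best counter-argument is that nothing in the SAP points to unequal exit in a double-blind 1:1 trial, and that equal exit leaves the comparison valid. That is correct, and the point is conditional for this reason. A reader might infer that early dropout or death always flatters an arm; the documents do not support that.

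A reader might also infer that mortality is affected in the same way. It is not. Under item 9(v) a patient who dies is a counted event, and deaths are displayed beside the non-fatal outcomes. An excess of deaths would be visible, so a claim that the plan hides harm goes too far.

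Section 7.1.1 defines dropout by a missing CT outcome without a known death. It does not say that event collection stops, and the protocol, which may settle this, is not shown. Nor does the SAP say that early leavers are scored as having no event. Both remain assumptions here, as does the use of the Van Elteren test for totals.

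Finally, the comparisons are exploratory, the detectable binary difference is 30 points, and section 7.2 compares dropout by arm and tabulates reasons for loss. A reader of the results would see an imbalance in dropout, but nothing in the plan carries it into the event comparison.

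**Conclusion.** The concern holds in conditional form. The plan makes no allowance for follow-up time when comparing non-fatal events. The comparison is biased if early exit or death differs between arms and events are not collected after exit. Under the assumed rates and a 10- to 20-point imbalance, the size is about 2 to 8 points on any event and 5 to 15% on totals, with a false-positive rate of about 6 to 11%. Rarer events would show smaller gaps in points. With equal exit there is no bias. For mortality, only dropout that hides later deaths matters.

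The effect is modest beside the 30-point detectable difference. It bears mainly on how event results are read and carried into a definitive trial. This is a worthwhile, inexpensive improvement and does not invalidate the plan.

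**What to change.** In section 7.1.2 item 9 and section 7.2, before treatment assignments are unblinded:

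1. Define each patient's follow-up from randomization to study exit, withdrawal or death, and state whether events were still collected after withdrawal.
2. Report the number of events, patient-years and events per patient-year by arm for each event type.
3. Compare time to first event, censored at exit and with death shown alongside as a competing event, by a log-rank test stratified by site and diabetes. Compare time to death in the same way.
4. Keep counts and percentages as description.
5. Treat a count model with log follow-up time as offset (negative binomial, or Poisson with robust errors) as optional, for outcomes with enough events, such as hospitalizations. With about 80 patients and few events it is less robust than a rank test.

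The cost is some programming and the assembly of withdrawal and first-event dates. The dropout definition uses only death and CT dates, so it does not supply them. The remaining limitation, that rates do not fully remove bias when exit is related to risk, should be stated with the results.

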7.1.3 Exploratory Outcomes

- 1) Biomarkers of inflammation: these biomarkers (listed in Section 6.4) will be assessed at baseline, four months, eight months, and study exit.
- 2) Clinical lab values: Hemoglobin, albumin, Kt/V, creatinine, lipid profile (HDL, LDL, triglycerides, and total cholesterol), and parameters of mineral metabolism (phosphate, calcium, PTH, and ALP) will be assessed monthly. Serum FGF-23 will be assessed at baseline, four months, eight, and study exit.
- 3) Concomitant medication assessment: prescription of concomitant medications (listed in Section 6.4) will be assessed monthly. Average dosage and total exposure across the study duration will be assessed for calcitriol, other vitamin D drugs, and calcium-based phosphate binders.
- 4) Changes in body composition: body composition measures (listed in Section 6.4; L3 slice of ST scan) will be assessed for muscle atrophy and adipose tissue at baseline and at study exit.
- 5) Vascular inflammation variables: these variables (listed in Section 6.4) will be assessed at baseline, four months, eight months and study exit.
- 6) Vitamin D Metabolites: these metabolites (listed in Section 6.4) will be assessed at baseline, four months, eight months, and study exit.

7.2 Analysis Methods

The feasibility outcomes will be presented descriptively overall as rates or proportions. In addition, compliance with study medication, dropout rate, and adherence to study protocol will be compared by arm. Reasons for loss-to-follow-up and non-compliance will be tabulated.

For the binary outcomes, we will provide counts and percentages by arm and compare arms by the Mantel-Haenszel test stratified by site and diabetes (or Fisher's Exact Test for outcomes with less than 20 events or non-events).

This study has many continuous outcomes that are far from normally distributed. For all continuous outcomes, we will report medians and quartiles by arm and compare arms by the Van Elteren test stratified by site and diabetes. Selected continuous variables may be depicted by clustered boxplots comparing the two arms over time. Biomarkers assessed at multiple time points will have both absolute value and change from baseline compared by arm at each time point.

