4.1 Trial Design

The current iPACK-HD pilot trial is a prospective randomized parallel two-arm double-blind 3-centre feasibility and exploratory phase II trial in adults with ESKD requiring dialysis who have a baseline CAC score ≥ 30 Agatston units (AUs). Eligible patients were randomly assigned 1:1 to either the experimental treatment group (10 mg of phylloquinone thrice weekly) or to a control group (matching placebo thrice weekly). The initial plan was to roll patients from this pilot feasibility trial into a full definitive phase II RCT. However, due to pragmatic considerations including challenges obtaining Canadian Institutes of Health Research (CIHR) funding, this study is now a stand-alone pilot feasibility and exploratory phase II trial. If the results of this trial suggest that a large scale definitive RCT is warranted, then the feasibility and preliminary results will be used to help support the design and funding application for the definitive trial.

The protocol for the planned definitive RCT is published in the Canadian Journal of Kidney Health and Disease.² The protocol for this pilot feasibility trial is a successful grant application from the March 2015 CIHR RCT committee.

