6.4 Baseline Characteristics

Baseline characteristics will be described by arm and overall using descriptive statistics only. Categorical variables will be described as counts (%). Continuous variables will be described as median [Q1 to Q3].

The following baseline patient characteristics will be described:

- Age, sex, ethnicity, CKD cause, number of comorbidities (0, 1, 2, >2), Charlson Comorbidity Index, weight, height, BMI, abdominal waist circumference, smoking history, parathyroidectomy, primary HD access site, primary HD access type, time from primary HD access installed to randomization, time from start of HD to randomization
- Baseline concomitant medication use
 - Calcium-based phosphate binders: calcium, calcium acetate, and calcium carbonate
 - Non-calcium-based phosphate binders: sucralfate, sevelamer hydrochloride (HCl), and lanthanum carbonate
 - Calcitriol
 - Vitamin D: ergocalciferol and cholecalciferol
 - Calcimimetic: cinacalcet HCl
 - HMG-CoA reductase inhibitors: atorvastatin calcium, fluvastatin sodium, lovastatin, pravastatin sodium, simvastatin, ezetimibe, rosuvastatin calcium, and amlodipine besylate/atorvastatin calcium
 - Angiotensin converting enzyme (ACE) inhibitors: benazepril HCl, captopril, perindopril erbumine, quinapril HCl, ramipril, enalapril, fosinopril sodium, lisinopril, and lisinopril/hydrochlorothiazide
 - Angiotensin II receptor blockers (ARBs): losartan potassium, irbesartan, candesartan cilexetil, telmisartan, eprosartan mesylate, and valsartan
 - Anti-platelet therapy: acetylsalicylic acid, clopidogrel bisulfate, and dipyridamole
- Baseline blood measures
 - Clinical lab values:
 - Hemoglobin, albumin, Kt/V, creatinine, and fibroblast growth factor-23 (FGF-23)
 - Lipid profile: high-density lipoprotein (HDL), low-density lipoprotein (LDL), triglycerides, and total cholesterol
 - Parameters of mineral metabolism: phosphate, calcium, parathyroid hormone (PTH), and alkaline phosphatase (ALP)
 - Vitamin K status: protein induced by vitamin K absence or antagonist II (PIVKA-II), growth arrest-specific 6 (Gas6), phylloquinone/vitamin K1 (PK), vitamin K2 (MK4), osteocalcin Gla, osteocalcin Glu, osteocalcin Gla to Glu ratio, percent of osteocalcin undercarboxylated, and dephosphorylated-uncarboxylated MGP (dpucMGP)
 - Biomarkers of inflammation: c-reactive protein (CRP), interleukin 6 (IL-6), leptin, insulin, glucose, homeostasis model assessment-insulin resistance (HOMA-IR)

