8.2 Validation of SAS Database and Analysis

The study Principal Investigator and Project Leader will sense check all results to make sure they are not highly suspicious and that all counts are consistent with the patient flow diagram.

A second statistician who did not perform the primary analysis will independently verify the patient flow counts and re-analyze the main secondary outcome of CAC progression (measured by percent change in Agatston and percent change in the volume calcium scores), as well as the biomarkers of vitamin K status and inflammation.

9 References

10 Appendix A: Statistical Analysis Plan (SAP) Checklist v 1.0 2019

Section/Item	Index	Description	Reported on page #
Section 1: Administrative information			
Trial and Trial registration	1a	Descriptive title that matches the protocol, with SAP either as a forerunner or subtitle, and trial acronym (if applicable)	1
	1b	Trial registration number	1
SAP Version	2	SAP version number with dates	1
Protocol Version	3	Reference to version of protocol being used	1
SAP revisions	4a	SAP revision history	1
	4b	Justification for each SAP revision	N/A
	4c	Timing of SAP revisions in relation to interim analyses, etc.	1
Roles and responsibility	5	Names, affiliations, and roles of SAP contributors	1, 3
Signatures of:	6a	Person writing the SAP	2
	6b	Senior statistician responsible	2
	6c	Chief investigator/clinical lead	2
Section 2: Introduction			
Background and rationale	7	Synopsis of trial background and rationale including a brief description of research question and brief justification for undertaking the trial	6
Objectives	8	Description of specific objectives or hypotheses	6
Section 3: Study Methods			
Trial design	9	Brief description of trial design including type of trial (e.g., parallel group, multi-arm, crossover, factorial) and allocation ratio and may include brief description of interventions	7

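### Serial biomarkers, CAC and valve scores are each tested on two scales with no stated lead; naming one lead and adjusting it for ranked baseline is a cheap improvement, not the correction of an error

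*SAP*

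**What the plan says.** Section 7.2 sets one method: "For all continuous outcomes, we will report medians and quartiles by arm and compare arms by the Van Elteren test stratified by site and diabetes". For serial markers it adds: "Biomarkers assessed at multiple time points will have both absolute value and change from baseline compared by arm at each time point".

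Section 7.1.2 gives CAC two change scales: "the percent and absolute change of the Agatston and volume calcium scores (CT scan) will be assessed at study exit vs. baseline". This covers six CAC measures. The aortic and mitral valves have the same pair, for example "Mitral valve calcification progression: the absolute and percentage change of the Agatston and volume calcium scores (CT scan". Section 7.1.3 sets the schedule for the inflammation markers: "these biomarkers (listed in Section 6.4) will be assessed at baseline, four months, eight months, and study exit". Appendix A, item 27b, marks covariate adjustment as N/A.

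The only hint of a lead lies outside section 7. Section 8.2, on independent verification, refers to "the main secondary outcome of CAC progression (measured by percent change in Agatston and percent change in the volume calcium scores". It does not choose between the two scores or say which of the six CAC measures is meant, and it names no scale for valves or biomarkers.

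Section 5.1 sets nominal significance at p<0.05 without multiplicity adjustment and allows optional use of false discovery rates. Abdominal aortic calcification and body composition have no stated pair of scales, so the point does not reach them.

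**The concern.** Two unadjusted tests of one quantity at one time point give two chances of a nominal positive, and section 7 has no rule for a disagreement. A false discovery rate can temper the p-values, but it does not say which scale is the result. Section 3.2 intends these preliminary results to support the design and funding of a definitive trial, so which one is read matters.

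Either scale can be the weaker one, depending on the correlation between baseline and follow-up, which the SAP does not give. A collected baseline can be used more efficiently than by subtraction or division alone.

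Percent change is also undefined when the baseline is zero. Section 4.1 requires "baseline CAC score ≥ 30 Agatston units (AUs"); that floor applies to the CAC score, not to each artery or valve. The section 8.2 scale may therefore not exist for every patient on every CAC measure.

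**Working it through.** **The plan's own figure.** Section 4.3 claims 80% power with 40 per arm at two-sided 0.05, for a difference of 0.63 SD (t-test) or a concordance of 0.68 (Wilcoxon).
- t-test: 0.63/√(2/40) = 2.817; Φ(2.817 − 1.96) = 80.4%. The noncentral t gives 79.5%.
- Wilcoxon (Noether): √(12 × 0.25 × 80) × 0.18 = 2.789; Φ(2.789 − 1.96) = 79.6%.

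Both reproduce.

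**Number of comparisons** (sections 6.4, 7.1.2 and 7.1.3, three post-baseline times). Vitamin K status: 8 × 3 + 1 (PIVKA-II, exit only) = 25. Inflammation: 6 × 3 = 18. Together 43 comparisons on two scales make 86 tests. With no effect, 86 × 0.05 = 4.3 nominal positives are expected, of which 43 × 0.05 = 2.15 fall on any one scale. If vascular inflammation (12 × 3 = 36) and vitamin D metabolites (12 distinct × 3 = 36) count too, 115 comparisons make 230 tests. CAC gives 6 measures × 2 scores × 2 scales = 24 tests, and the valves 2 × 2 × 2 = 8.

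**Normal theory for adjustment.** The variance factor f is 1 for the follow-up value, 2(1 − ρ) for change and 1 − ρ² for baseline-adjusted. Power = Φ(0.63/√(2f/40) − 1.96).
- ρ = 0.3: value 80%, change (f = 1.4) 66%, adjusted (f = 0.91) 84%.
- ρ = 0.5: value 80%, change (f = 1.0) 80%, adjusted (f = 0.75) 90%.
- ρ = 0.7: value 80%, change (f = 0.6) 95%, adjusted (f = 0.51) 98%.

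**Simulated rank tests.** N = 80 in six assumed strata (18, 18, 12, 12, 10, 10), 1:1 within stratum, log-normal data with log SD 0.5 to 1.0 and an effect of 0.63 SD on the log scale. The adjusted test ranks change and baseline within stratum, removes one pooled slope on baseline rank, and applies the stratified test to the residuals. Biomarker change from baseline is taken as absolute change. Power in %:

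| Assumed correlation | Value | Absolute change, effect lowers / raises | Percent change | Percent change, rank-adjusted |
|---|---|---|---|---|
| 0.3 | 74–75 | 45–52 / 61–63 | 60–61 | 74–75 |
| 0.5 | 74–75 | 56–65 / 75–76 | 74–75 | 83 |
| 0.7 | 74–75 | 76–85 / 91–93 | 92 | 94–95 |

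Against the same change unadjusted, adjustment gains about 0 to 18 points. The largest gain is for absolute change at correlation 0.3 with a lowering effect and log SD 1.0: 45 + 18 = 63%. That is still 75 − 63 = 12 points below the value test. Across the cells at 0.3, adjusted absolute change trails value by about 3 to 12 points.

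At correlation 0.85 / 0.9 / 0.95, with shifts of 0.35 / 0.3 / 0.2 SD, adjusted against unadjusted percent change is 78 v 76, 81 v 80 and 75 v 75%.

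**No effect.** Value or absolute change is significant in about 8 to 10%, and absolute or percent change in about 6 to 8% (7 to 9% in a CAC model with a floor at 30 AU). Each single test stays near 5%. With a true 0.63 SD effect, value and change disagree on significance in about 24 to 30% of trials, and in 23 to 45% in the log-normal cells.

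**Where the chosen scale loses.**
- CAC model with a multiplicative effect (log ratio −0.2, log-scale change SD 0.35): absolute change 58%, percent change 70%, adjusted percent change 70%, exit score adjusted for baseline 61%.
- Additive progression on skewed scores: planned absolute change 75 to 79%, adjusted percent change 64 to 74%, a loss of about 4 to 14 points; a second set of runs gave 3 to 11.
- Zero baselines, lowering effect, correlation 0.5 to 0.95: adjusted absolute change against planned percent change is −7 to +6 points with 5% zeros and −1 to +16 with 30%. The worst cases, at log SD 1.5, are −12 and −1. With 30% zeros, percent change exists for about 0.7 × 80 = 56 patients.

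**The case against.** The best case for leaving the plan alone is that nothing in it is wrong. Feasibility is primary, the arm comparisons are declared exploratory, and section 5.1 openly leaves p-values unadjusted while promising to weigh both error types. The protocol text quoted in section 4.3 says the pilot will not be used to determine effect size. All of that stands and keeps the severity low.

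Three further objections stand in part.
- Keeping the planned tests as supportive does not shrink the test count. A reader might infer that 86 tests become 43. They do not: the gain is a rule for reading, and multiplicity across markers, visits, vessels and scores remains.
- For CAC percent change, the outcome section 8.2 calls the main secondary one, adjustment may add nothing (70 v 70% in the CAC model). There the benefit is the named lead.
- A percent-change lead for every outcome might look almost free. It is not, given the 3 to 14 point loss under additive progression. The SAP does not say which effect shape applies.

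What does not stand is that this is mere preference. Section 1.3 says the SAP is to fix exactly what analysis will be performed, and section 7 leaves open which of two results is read.

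**Conclusion.** The point holds as a low-severity improvement. Section 7 should say which scale leads, and a stratified rank ANCOVA uses the collected baseline better than change alone when correlation is low to moderate. At correlation 0.9 or above, or with additive progression, the gain is about nil and the loss against the same unadjusted scale is at most about 1 point.

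Three stronger readings are not supported.
- *The planned tests are invalid.* Each holds its nominal level.
- *No lead is named anywhere.* Section 8.2 points to percent change for CAC.
- *Baseline is ignored.* Change and percent change use it; what is absent is adjustment for it as a covariate.

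Correlations, log SDs, effect shape, stratum sizes and zero shares are all assumed, because the SAP gives none. The power figures show a range and do not forecast this trial.

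**What to change.** Before unblinding:

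1. In section 7, name one lead comparison per outcome and time point and mark the other planned tests as supportive.
   - Total CAC: percent change, in line with section 8.2, with a choice between Agatston and volume.
   - Serial biomarkers: the change from baseline already planned in section 7.2.
   - Single arteries and valves: absolute change, which keeps every patient with both scans when the baseline is zero.
2. Run each lead as a rank ANCOVA of that change on ranked baseline, stratified by site and diabetes. Do not use the exit value as a blanket response: in the CAC model it gave 61% against 70% for percent change. Name the test in section 7.2.1 and update item 27b.
3. State the downsides: a percent-change lead can trail absolute change if progression is additive; an absolute-change lead can trail percent change if effects are multiplicative; and an adjusted absolute-change lead can trail the value test at low correlation.
4. A minor separate point: Appendix A, item 18, refers to confidence intervals, but section 5.1 plans none. Add a stratified Hodges-Lehmann shift with a 95% CI, or correct the item.

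The cost is SAP wording and some SAS code, with no new data. The power cost is the possible loss to the scale not chosen, as sized above.
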